Statistical Analysis Plan: Emotion-Diet Interactions in Pregnancy (PREDIP)

NCT04430439

Date of document: 4/6/2020

STATISTICAL DESIGN AND POWER ANALYSIS

Statistical Design: The statistical approach for each of the Specific Aims will be performed as follows:

Aim 1a: A cross-over study design will test the hypothesis that experimental exposure to a standardized psychosocial stress task will potentiate the postprandial metabolic response to the standardized meal. Each subject will represent her own control within the assigned meal group (low or high GI). A paired-samples t-test will be employed, using the model: $E[Y_i] = \Delta AUC_i = (AUC_i)v1 - (AUC_i)v2$

where Y_i denotes the outcome measurement (change in $AUC_{glu/ins}$ or AUC_{FFA}) on maternal i, and AUC_i denotes the AUC for either metabolic outcome at a given laboratory visit; v1 or v2. As such, a test of the hypothesis that the above equations equals 0, represents a test that the effect of acute psychosocial stress exposure does not moderate the postprandial response to a standardized meal. A sensitivity analysis to estimate the difference in response by randomization sequence will ensure that the order of protocols does not confound the results.

Aim 1b: To explore the difference in the postprandial metabolic response following acute psychosocial stress exposure across meal types (low vs high GI), an independent sample t-test will be employed to compare the mean $AUC_{glucose/insulin}$ between the high GI and low GI groups.

Aim 2: To determine whether individual variation in biological stress reactivity (i.e., $AUC_{cortisol}$ and AUC_{HRV}) moderates the effect of acute psychosocial stress on the metabolic response to the standardized meal, a general linear model accounting for within subject correlation will be employed, according to the model:

$$E[Y_{ij}] = \beta_0 + \beta_1 STRESS_{ij} + \beta_2 REACT_{ij}$$

where Y_{ij} denotes the outcome change in the AUC_i on maternal i, STRESS denotes the condition of exposure (stress vs no stress) to mother i on laboratory visit j, and REACT denotes stress reactivity, measured by $AUC_{cortisol}$ or AUC_{HRV} . A test of $H_0: \beta_1 = 0$ will test the hypothesis that mean AUC_i ($AUC_{glu/ins}$ and AUC_{FFA}) differs by stress condition after adjustment for stress reactivity. An exchangeable correlation matrix will be assumed in the model.

Power Analysis: The primary outcome of the proposed research is the difference in the postprandial glucose/insulin response to a standardized meal (of either low or high GI) between the stress and non-stress conditions. Utilizing a cohort of 40 women in each meal group, it is estimated that the proposed study will have approximately 80% power to detect a 0.44 standard deviation difference in the mean within subject change in postprandial metabolic response ($AUC_{glu/ins}$ and AUC_{FFA}), associated with the introduction of the stress paradigm.

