#### **C.6 Visit Protocols and Study Measures.**

**C.6.1 Screening & consent visit:** This visit will entail informed consent and confirmation of full study eligibility in order to proceed with subsequent test visits. An interview with a trained research coordinator will determine whether any medical conditions, psychiatric disorders or medication usage may render them ineligible to continue participation. Peripheral blood glucose will be tested by glucometer to detect potential undiagnosed diabetes (random glucose  $\geq 200$  mg/dl). Those considered eligible to continue participation will be provided instructions to complete an online survey at home before their first test study visit. This will assess maternal sociodemographic factors, psychosocial states (e.g. chronic stress, anxiety, resiliency) and behaviors (e.g. usual dietary intake, sleep, exercise habits). A standardized healthy evening meal of medium GI will be delivered to participant homes prior to each test study visit to control for recent dietary influences on morning glycemia.

**C.6.2 Test visit 1:** Participants will attend the research lab facility in the morning following an overnight fast (minimum 8 hours), between 20-22 week's gestation. A research nurse will place an indwelling catheter to the antecubital vein to allow frequent blood sampling throughout the test period with minimal discomfort. After catheter placement, women will rest comfortably for 30 mins. A fasting blood and saliva sample will be collected immediately prior to consumption of the assigned standardized breakfast meal, followed by performance of either the psychosocial stress or non-stress protocol. Postprandial blood and saliva samples will be collected at +30 (pre-task), 45 (post-task), 60, 75, 90, 120 & 150 mins. A heart rate variability monitor will be worn throughout the

duration of each test study visit. Immediately pre- and post-task protocols, participants will complete questionnaires to assess momentary affective state and self-appraisal of upcoming/completed tasks.

**C.6.3 Test visit 2:** All participants will be allowed a 1-week “wash-out” period before returning to the research lab for test visit 2. Participants will undergo the same protocol as test visit 1 with the same meal assignment, except with the alternative stress/non-stress paradigm as performed on visit 1.

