**C.6.7 Randomization procedures:** A biostatistician will generate the randomization sequence for a 1:1 assignment to the meal group arms (*i.e.* high GI or low GI), and for the sequence of stress or non-stress protocols at the test study visits (*i.e.* stress at v1 and non-stress at v2, or non-stress at v1 and stress at v2) within each arm. Randomization sequences will be contained in sealed, opaque envelopes labeled by sequential study IDs and only revealed by research coordinators after completion of a screening visit for a fully eligible participant.

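### Aim 1a writes the primary paired difference as visit 1 minus visit 2, although task order is randomised across visits, so with balanced sequences the stress effect cancels

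*SAP*

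**What the plan says.** The Aim 1a paragraph of the SAP sets a paired test within each meal group: "Each subject will represent her own control within the assigned meal group (low or high GI). A paired-samples t-test will be employed". The difference to be tested is "AUC_i)v1 - (AUC_i)v2", and the labels are defined by visit: "AUC_i denotes the AUC for either metabolic outcome at a given laboratory visit; v1 or v2". The SAP then says that testing this quantity against zero tests the effect of acute stress. It adds a check on order: "A sensitivity analysis to estimate the difference in response by randomization sequence will ensure that the order of protocols does not confound the results".

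Protocol C.6.7 uses the same labels for the visits in time order and randomises the task across them within each meal arm: "stress at v1 and non-stress at v2, or non-stress at v1 and stress at v2". The SAP's Power Analysis gives the primary outcome as the difference between the stress and non-stress conditions. It claims about 80% power for 0.44 SD of the within-woman change with 40 women per meal group.

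**The concern.** The two documents use v1 and v2 for the same thing, the first and second laboratory visit. Stress falls at v1 in one sequence and at v2 in the other, so it enters v1 minus v2 with opposite signs. The average of that difference over a balanced group carries no stress effect. What remains is any systematic change between visits, such as familiarity with the laboratory or a further week of gestation.

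An analysis programmed from the formula would have almost no chance of detecting the planned effect, and it could report a visit-order difference as a stress effect. The order check adds a second hazard. If it compares v1 minus v2 between the two sequences, that comparison contains the stress effect, yet it carries the label of a confounding check.

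**Working it through.** **Inputs.** From the SAP: 40 women per meal group, effect 0.44 SD of the within-woman difference, power about 80%. From protocol C.6.7: task order randomised within arm. Assumed because the documents do not state them: two-sided alpha 0.05, no dropout, and a 20/20 split of sequences (no blocking is described). Differences are scaled to SD 1 within sequence.

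**The plan's own figure.** For a one-sample test on differences, 0.44 × √40 = 2.783. The normal approximation gives Φ(2.783 − 1.960) = Φ(0.823) = 79.5%, which matches the stated figure. The exact noncentral t on 39 df gives 77.4%. The power statement therefore corresponds to a stress-minus-non-stress difference within one meal group.

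**Expected value of the formula as written.** Let tau be the stress effect and pi the visit-order difference (visit 1 minus visit 2 with the task held fixed).
- Stress first: expected v1 − v2 = pi + tau
- Non-stress first: expected v1 − v2 = pi − tau
- Over the group: pi + tau × (n_stress-first − n_nonstress-first)/n

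At 20/20 the second term is 0.44 × 0/40 = 0. At 24/16 it is 0.44 × 8/40 = 0.088 SD.

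**Rejection rate of the literal test** (simulation, 200,000 trials per row):

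| tau (SD) | pi (SD) | Split | Literal v1 − v2 | Coded by condition |
|---|---|---|---|---|
| 0.44 | 0 | 20/20 | about 3% | 77% |
| 0.88 | 0 | 20/20 | 0.9% | above 99% |
| 0.44 | 0 | 24/16 | 6% | 77% |
| 0 | 0.3 | 20/20 | 46% | 4% |
| 0 | 0.44 | 20/20 | 77.5% | 3% |

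The rate falls below 5% in the first row because the cancelled effect is still in the variance: 1 + 0.44² × 40/39 = 1.20. A larger stress effect therefore makes rejection rarer, as the second row shows. For the fourth row, the noncentrality is 0.3 × √40 = 1.897 on 39 df, which gives 45.7%, in agreement with the simulation. Under simple unblocked randomisation with tau = 0.44, the literal test rejects 5.0% of the time.

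**The sequence comparison.** Comparing v1 − v2 between sequences gives (pi + tau) − (pi − tau) = 2 × tau = 0.88 SD. Its standard error is √(1/20 + 1/20) = 0.316, and 0.88/0.316 = 2.783 on 38 df, so power is 77.4%. The stress effect is recoverable there, under the wrong name.

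**After recoding.** The stress-minus-non-stress difference has expectation tau + pi in one sequence and tau − pi in the other. At 20/20 its mean is tau, but pi stays in the error: for pi = 0.3 the variance is 1 + 0.09 × 40/39 = 1.09, and simulated power is 74.6%. With sequence coded +0.5/−0.5 the intercept is tau and the slope is 2 × pi. The test of the intercept has 38 df and 77.4% power whatever pi is. With pi = 0 the term costs less than 0.1 point (77.45% on 39 df, 77.39% on 38 df).

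**Fasting covariate.** Adding the stress-minus-non-stress fasting difference (uncentred) as well as the sequence term leaves 37 df and multiplies the SD by √((1 − rho²) × 37/36). Power is 76.2%, 77.9%, 80.0% and 87.0% at rho = 0, 0.2, 0.3 and 0.5, against 77.4% without it. Break-even is at rho of about 0.17. The documents give no value of rho.

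**The case against.** The strongest reply is that this is notation. The sentence after the formula says the test concerns acute stress, the Power Analysis speaks of conditions, and Aim 2 carries a stress indicator for each visit. An analyst who reads all of this would code by condition. That stands as the likelier intent. A reader might infer from the formula that the trial is bound to miss a stress effect, or that the sponsor means to analyse by visit. The documents do not support either inference. The 3% and 46% figures describe the formula taken literally, and the 46% also needs a visit-order difference that is assumed. It remains true that both documents define v1 and v2 as visits, and that this is the only stated rule for the primary test.

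A second reply is that the planned order analysis could recover the effect. As shown above it could, if it compares v1 − v2 between sequences. But the SAP does not give its form, and it is presented as a safeguard against confounding by order. A true stress effect could then be read as an order problem.

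A reader might also infer that leaving the fasting value out of Aim 1a is an error. The protocol does provide for it: "A fasting blood and saliva sample will be collected immediately prior to consumption of the assigned standardized breakfast meal", and visit 2 repeats the procedure. But a paired t-test coded by condition is valid without a covariate, so the omission affects precision only. The gain depends on an unstated correlation, and the SAP does not say whether AUC is total or incremental. Women may also know their task before the fasting draw, since the assignment is "only revealed by research coordinators after completion of a screening visit for a fully eligible participant" and visit 2 always uses the other task. If anticipation moved the fasting value, adjustment would bias the comparison. That argues against making the adjusted test primary.

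**Conclusion.** Wrong as written, and probably a labelling slip. The Aim 1a formula does not estimate the quantity that the SAP names as primary. With 40 women per meal group, 20/20 sequences and two-sided alpha 0.05 (the last two assumed), the literal test rejects about 3% of the time at 0.44 SD, against 77% coded by condition. With no stress effect and an assumed visit-order difference of 0.3 SD, it rejects about 46% of the time. Modest imbalance does not rescue it (6% at 24/16).

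A reader might take the gap between 77.4% and the stated figure as a power error. It is not: the normal approximation gives 79.5%, consistent with approximately 80%. The point concerns the definition of the outcome. The choice of a paired t-test and the sample size are not in question here.

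**What to change.** 1. In Aim 1a, replace the visit contrast by AUC(stress) minus AUC(non-stress) for each woman, and keep the paired t-test of that difference within each meal group as primary.
2. Include sequence, coded +0.5/−0.5, and test the intercept, or report that model alongside the t-test. State in advance which is primary. The term removes a visit-order difference from the error (77.4% power against 74.6% if that difference is 0.3 SD).
3. Write out the order sensitivity analysis on the recoded difference, so that its sequence coefficient is read as twice the visit-order difference and cannot be confused with the stress effect.
4. If a fasting-adjusted analysis is wanted, list it as optional and supportive.

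The cost is a few lines of SAP text and code, and one degree of freedom for the sequence term. No samples, visits or procedures change.

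### The Aim 1a paired t-test drops every woman who misses visit 2, together with her measured visit 1 AUC; if return depends on that AUC and differs by sequence, the stress contrast can be biased

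*SAP*

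**What the plan says.** SAP, Statistical Design, Aim 1a: each woman serves as her own control within her meal group, and "A paired-samples t-test will be employed" on the difference between her two AUCs. The only sensitivity analysis named for this aim compares response by randomisation sequence.

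SAP, Power Analysis: "The primary outcome of the proposed research is the difference in the postprandial glucose/insulin response to a standardized meal" between the stress and non-stress conditions. The calculation takes 40 women per meal group and claims "approximately 80% power to detect a 0.44 standard deviation difference in the mean within subject change". No allowance for lost pairs is mentioned.

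Protocol C.6.3: there is a wash-out of one week "before returning to the research lab for test visit 2", where the same procedures are repeated with the other task. Protocol C.6.7: the order is randomised within each meal arm ("stress at v1 and non-stress at v2, or non-stress at v1 and stress at v2").

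Neither document mentions non-return, missing visits, an analysis population, imputation or replacement of women.

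**The concern.** A paired t-test needs both AUCs. A woman who attends only visit 1 may have given all eight blood samples there, yet contributes nothing to the primary analysis.

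The two sequences have different experiences before women decide whether to come back. Under Protocol C.6.4, one has faced a speech before an evaluating panel, filming and mental arithmetic; the other has had a relaxed conversation. Both are asked to return for another fasting, catheterised session. Different return rates by sequence are therefore plausible, though the documents do not show them.

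Randomising the order protects the contrast only if those who return remain comparable across sequences. If return is related to visit 1 AUC, and more so in one sequence, the completers' mean difference moves away from the true effect and crossing over does not cancel the shift. The planned comparison by sequence could show a discrepancy, but could not tell it from a period or carry-over effect, and it restores no lost data.

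**Working it through.** **1. The plan's own figure.** Inputs from the SAP: 40 pairs per meal group and a difference of 0.44 SD of the within-woman change. Alpha is not stated; two-sided 0.05 is assumed.

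Power = Φ(0.44 × √40 − 1.96) = Φ(0.823) = 79.5%. The stated figure of about 80% reproduces by the normal approximation with all 40 pairs complete. The noncentral t gives 77.5%.

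**2. Lost pairs, no bias.** Assume 20 women per sequence in each meal group. If 20% of the stress-first women do not return, 4 pairs are lost and 36 remain: Φ(0.44 × √36 − 1.96) = Φ(0.680) = 75.2%.

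**3. Bias when return depends on visit 1 AUC.** Nothing here is in the documents; all of it is assumed. The AUC has SD 1 and between-visit correlation ρ of 0.5 or 0.7. The true effect is 0.44 × √(2(1−ρ)), that is 0.440 or 0.341. The sequences are equal in size. Women in the upper tail of visit 1 AUC fail to return with probability 2/3, and the tail fraction is set to give the wanted loss p.

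Let m be the mean standardised visit 1 AUC of the women lost, which equals φ(z)/q for an upper tail of fraction q = 1.5p:
- p = 10%: q = 0.15, m = 1.554, p × m = 0.155
- p = 20%: q = 0.30, m = 1.159, p × m = 0.232
- p = 30%: q = 0.45, m = 0.880, p × m = 0.264

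Losing high visit 1 values lowers the stress-minus-non-stress mean in the stress-first sequence (S) and raises it in the other (N). Pooling completers gives

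bias = −(1−ρ) × (p_S m_S − p_N m_N) / (2 − p_S − p_N).

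| Loss S / N | Bias, ρ = 0.5 | Share of effect | Bias, ρ = 0.7 | Share of effect |
|---|---|---|---|---|
| 20% / 0% | −0.5 × 0.232/1.8 = −0.064 | 85% | −0.3 × 0.232/1.8 = −0.039 | 89% |
| 30% / 0% | −0.5 × 0.264/1.7 = −0.078 | 82% | −0.3 × 0.264/1.7 = −0.047 | 86% |
| 20% / 10% | −0.5 × (0.232 − 0.155)/1.7 = −0.022 | 95% | −0.3 × (0.232 − 0.155)/1.7 = −0.013 | 96% |
| 20% / 20% | 0 | 100% | 0 | 100% |
| 0% / 20% | +0.064 | 115% | +0.039 | 111% |

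Simulation with 400,000 women per scenario agrees for the unequal-loss rows in which the stress-first sequence loses more. In those scenarios maximum likelihood using all visit 1 data recovers about 100%. Loss unrelated to AUC gives no bias by either method.

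A gentler rule (logistic, odds ratio 2 to 3 per SD of visit 1 AUC, ρ from 0.3 to 0.7, 10–30% loss in the stress-first sequence only) gives a completers' estimate of 0.43 to 0.38 against a true 0.44, that is 98% to 86%.

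**4. Effect on power.** With 20% against 0% loss, completers estimate about 0.85 to 0.89 of 0.44, that is 0.376 to 0.390 SD. At 36 pairs power is Φ(0.376 × 6 − 1.96) = 62% to Φ(0.390 × 6 − 1.96) = 65%, against 75% from lost pairs alone.

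**5. When loss follows the woman's own difference.** Apply the same tail rule to her stress-minus-non-stress difference (SD 1), 20% against 0%. The completers' bias is −0.232/1.8 = −0.129, leaving (0.44 − 0.129)/0.44 = 71%. By simulation the all-data likelihood estimate reaches only about 74% at ρ = 0.5 and 71% at ρ = 0.7.

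**The case against.** The strongest case against is that the documents give no evidence of the mechanism. Plasma is stored and assayed later (Protocol C.6.6), and nothing suggests that a woman senses her glucose, insulin or FFA response. If she stays away because she was distressed, and distress is unrelated to AUC, pairs are lost but nothing is biased. Non-stress-first women also face a second catheterised visit and still have the stress task ahead, so loss could be similar in both sequences or higher in theirs. The bias is also small beside the sampling error: 0.064 SD against a standard error of 1/√36 = 0.167 SD in one meal group. All of this stands, and it limits the claim about size. It does not supply a rule for the woman with one visit.

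A reader might infer three stronger things, none of which the documents support.
- **That the completers' analysis will understate the stress effect.** This needs more loss among stress-first women and a link with high AUC. The reverse pattern overstates the effect, as the last row of the table shows.
- **That the SAP already has a model that keeps one-visit women, because for Aim 2 "a general linear model accounting for within subject correlation will be employed".** The Aim 2 outcome is worded as a change in AUC, which a woman with one visit may not have. An exchangeable working correlation could also mean generalised estimating equations, which without weighting are not generally valid when loss depends on observed AUC.
- **That a mixed model cures the problem.** Step 5 shows that it does not when loss follows the woman's own stress effect.

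**Conclusion.** The point holds in limited form. The stated method excludes one-visit women, no other handling is given, and a better method costs little. Bias arises only if return is related to the AUC and the pattern differs by sequence; its direction and size cannot be known from the documents. The 82–89%, 95–96% and 100% figures illustrate assumed loss rates, correlations and a selection rule, and do not predict what will happen. Lost pairs reduce power whatever the cause, and the SAP's power figure has no margin for them.

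Talk of under- or overstatement presumes a stress-minus-non-stress contrast, as in the SAP's power section. The Aim 1a formula is printed as visit 1 minus visit 2, which under balanced order averages the stress effect towards zero even with full attendance. That is a separate matter and has to be settled first.

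**What to change.** In SAP Aim 1a, before outcome data are examined:
1. Define the contrast as stress minus non-stress.
2. Make the main analysis, within each meal group, a likelihood-based linear mixed model on the AUC at each attended visit, with fixed effects for condition and visit and a random woman effect. Include every randomised woman with at least one test visit.
3. Keep the paired t-test as a completers' sensitivity analysis.
4. Report non-return by sequence and meal group.
5. Add a sensitivity analysis for loss that depends on unobserved response, for example shifting the missing visit 2 AUCs over a stated range, separately by sequence.

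The cost is SAP wording and a few lines of code. With complete data the model gives essentially the same within-woman contrast as the paired test, adjusted for visit. Its limits should be stated: it removes bias only when loss is explained by observed AUCs, it helps little if loss follows the woman's own stress effect (hence item 5), and it cannot replace the information in lost second visits.

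### The Aim 1a primary test subtracts visit 2 from visit 1, but stress order is randomised, so the stress effect cancels and only a visit effect is tested

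*SAP*

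**What the plan says.** SAP, Statistical Design, Aim 1a: "A paired-samples t-test will be employed, using the model" ΔAUC = "AUC_i)v1 - (AUC_i)v2", where "AUC_i denotes the AUC for either metabolic outcome at a given laboratory visit; v1 or v2". The SAP then says that testing this quantity against zero "represents a test that the effect of acute psychosocial stress exposure does not moderate the postprandial response to a standardized meal". As a safeguard on order it adds: "A sensitivity analysis to estimate the difference in response by randomization sequence will ensure that the order of protocols does not confound the results". The Aim 1a model has no term for condition, sequence or period.

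Protocol C.6.7 uses the same labels for the two test visits and randomises their content within each meal arm: "stress at v1 and non-stress at v2, or non-stress at v1 and stress at v2". Protocol C.6.3 says that visit 2 repeats visit 1 with the same meal, "except with the alternative stress/non-stress paradigm as performed on visit 1".

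The SAP's Power Analysis section defines the primary outcome as a comparison of the stress and non-stress conditions. It gives about 80% power for a 0.44 SD within-woman effect with 40 women per meal group.

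**The concern.** The visit number does not identify the condition. For a woman given stress first, visit 1 minus visit 2 is stress minus non-stress; for a woman given stress second, it is the reverse. Averaging the two kinds of difference removes the effect that the trial was set up to find. What remains is any systematic difference between visits, such as a further week of gestation or familiarity with the catheter and laboratory.

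Two wrong conclusions are possible on the primary outcome: a real stress effect is missed, or a visit effect is reported as a stress effect. The sequence check could add a third, because applied to this same difference it would pick up the stress effect and label it confounding.

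**Working it through.** **Inputs.** 40 women per meal group, a 0.44 SD effect and about 80% power (SAP, Power Analysis). The two sequences come from Protocol C.6.7. Three assumptions are needed. The documents give no alpha or sidedness, so 0.05 two-sided is used. The 1:1 ratio is explicit for meal arms and is read as applying to sequence too, giving 20/20. No dropout is assumed.

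**The SAP's own figure.** For a paired stress minus non-stress difference, the normal approximation gives Φ(0.44 × √40 − 1.960) = Φ(2.783 − 1.960) = Φ(0.823) = 0.795. The required n is ((1.960 + 0.842)/0.44)² = 40.5. The noncentral t gives 0.774. So the stated power is reproduced, and it belongs to stress minus non-stress.

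**Algebra.** Let τ be the stress effect, π the visit 1 minus visit 2 effect, and p the share of women with stress at visit 1.

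| Difference | Stress first | Stress second | Overall mean | Stress-first mean minus stress-second mean |
|---|---|---|---|---|
| Visit 1 − visit 2 | τ + π | −τ + π | (2p − 1)τ + π | 2τ |
| Stress − non-stress | τ + π | τ − π | τ + (2p − 1)π | 2π |

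At p = 0.5 the written mean is π alone.

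**Simulation.** 40,000 trials per row, n = 40, SD of the within-woman difference set to 1. Entries are rejection rates.

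| τ | π | Sequences | Visit 1 − visit 2 (as written) | Stress − non-stress, paired t | Visit 1 − visit 2, compared between sequences |
|---|---|---|---|---|---|
| 0.44 | 0 | 20/20 | 3.2% | 77.4% | 77.4% |
| 1.0 | 0 | 20/20 | 0.6% | 100% | 100% |
| 0 | 0.44 | 20/20 | 77.5% | 3.3% | 5.0% |
| 0.44 | 0.44 | 20/20 | 71.3% | 71.5% | 77.4% |
| 0.44 | 0 | 22/18 | 4.0% | 77.5% | 76.8% |
| 0.44 | 0 | 26/14 | 9.5% | 77.5% | 73.7% |

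The first row falls below 5% because the stress effect enters the written test only as noise. The expected sample variance of the differences becomes 1 + 0.44² × 40/39 = 1.199, while the mean still varies as if it were 1. A larger stress effect therefore makes rejection rarer, as the second row shows.

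Unequal sequences leave only a small remnant. At 22/18, (2 × 0.55 − 1) × 0.44 = 0.044 SD; at 26/14, (2 × 0.65 − 1) × 0.44 = 0.132 SD. Unrestricted 1:1 randomisation of sequence gives about 4.9% rejection.

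The last column has two meanings. Half the between-sequence difference in visit 1 − visit 2 is the period-adjusted estimate of τ. Read as an order check, the same comparison would signal order confounding in 77% of trials that have a true 0.44 SD stress effect and no visit effect at all.

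**The case against.** The strongest reply is that this is a labelling slip. The Power Analysis section names the stress versus non-stress contrast, Aim 1a says each woman is her own control, and the stated power matches that contrast. The SAP never says first or second visit; the explicit ordering is in a protocol dated 10/20/2022, against 4/6/2020 for the SAP. Aim 2 indexes visits by j, so its separate STRESS term does not strictly settle what v1 and v2 mean in Aim 1a.

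The intent is probably as described. But the SAP itself defines the labels as laboratory visits, recognises a randomised order through its sequence check, and nowhere recodes visit as condition. An analyst who follows the text computes the wrong primary contrast.

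Two narrower points stand in part:

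- The SAP does not say which response is compared by sequence. If it is stress minus non-stress, the comparison gives 2π and is a proper period check. The inversion arises only if the visit 1 − visit 2 difference, the one response Aim 1a defines, is carried into it.
- Once the difference is redefined, balanced sequences make its mean unbiased without a period term, so period adjustment is not what cures the error. It still has value. At τ = π = 0.44 it raises power from 71.5% to 77.4%, and at 22/18 it removes a bias of 0.10 × 0.44 = 0.044 SD.

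**Conclusion.** The concern holds, and the formula must be corrected before analysis. As written, the primary test has essentially no power for the stress effect (3.2% against 77.4% at 0.44 SD) and would reject in 77.5% of trials with a 0.44 SD visit effect and no stress effect.

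The cancellation is exact only with equal sequence numbers, but moderate imbalance does not rescue the test: 9.5% rejection even at 26/14. The rates assume two-sided 5% and no dropout. The 0.44 SD visit effect is hypothetical, because the documents give none. The stated power and sample size are not affected, since they already rest on stress minus non-stress.

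**What to change.** 1. In SAP Aim 1a, define ΔAUC for each woman as AUC at her stress visit minus AUC at her non-stress visit, for each metabolic outcome.
2. Estimate its mean with adjustment for period. Either average the two sequence-specific means, or fit a mixed model with STRESS, PERIOD and a random effect for woman.
3. Replace the sequence sensitivity analysis with the reported period estimate. State that the visit 1 − visit 2 difference compared between sequences is not an order check, because it carries twice the stress effect.
4. State alpha and sidedness alongside the power statement.

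The cost is a few lines of SAP wording, one line of code and one degree of freedom for period. No new data are needed, and the sample size stays as planned.

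### Aim 1a randomises task order but leaves visit out of the paired t-test, and the sequence check cannot guarantee freedom from order effects

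*SAP*

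**What the plan says.** Protocol C.6.7 randomises women to a meal arm "and for the sequence of stress or non-stress protocols at the test study visits", so in each arm the order is "stress at v1 and non-stress at v2, or non-stress at v1 and stress at v2". The 1:1 ratio is stated for the meal arms. Blocking of the sequence is not mentioned.

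The SAP, under Statistical Design, Aim 1a, states: "A paired-samples t-test will be employed, using the model". The model that follows is the within-woman difference between the two visits, where "AUC_i denotes the AUC for either metabolic outcome at a given laboratory visit; v1 or v2". It contains no term for visit or sequence. Order appears once more, in a sensitivity analysis that estimates how the response differs between sequences and that, the SAP says, "will ensure that the order of protocols does not confound the results". The SAP does not give the contrast, the model, any threshold, or what follows from the result.

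Protocol C.6.3 sets a 1-week wash-out between the test visits. The SAP's power statement rests on 40 women per meal group and 0.44 SD of the within-woman change.

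**The concern.** A visit effect is plausible. Visit 1 is the woman's first session with the catheter and the laboratory, and visit 2 falls at least a week later in pregnancy. Randomising the order makes it possible to remove such an effect from the stress comparison, but the planned test does not do so.

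Two things are at stake. First, an unmodelled visit effect inflates the standard error and, if the two sequences differ in size, shifts the estimate. Second, the SAP claims a protection that one sequence comparison cannot give. A reader of the results could take a reassuring check as proof that order played no part.

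**Working it through.** **Inputs.** From the documents: 40 women per meal group, 0.44 SD of the within-woman change, about 80% power, order randomised within arm. Assumed, because not stated: two-sided alpha 0.05; visit effects of 0.1 to 0.5 SD of the paired difference; within-woman correlation 0.5 to 0.7; the sequence splits below.

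**The plan's own figure.** Normal approximation: Φ(0.44√40 − 1.96) = Φ(0.823) = 79.5%, which matches the stated figure. The exact paired t-test (39 df) gives 77.4%. Both assume no visit effect.

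**Model.** Sign each difference as stress minus non-stress. Let τ be the stress effect, π the visit-1-minus-visit-2 effect, λA the carry-over into visit 2 when stress comes first, and λB when it comes second, with the SD of a paired difference set to 1.
- Stress first: mean difference = τ + π − λA.
- Stress second: mean difference = τ − π + λB.

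**Equal sequences (20/20).** With no carry-over, π cancels from the overall mean, so there is no bias. It does not cancel from the sample variance, whose expectation is 1 + π²·40/39. Power is then approximately Φ(0.44√40 − 2.023·√(1 + π²·40/39)), where 2.023 is the critical value on 39 df. Simulation agrees with the formula to the nearest point or so.

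| Visit effect (SD) | Formula | Simulated, no visit term | With visit term |
|---|---|---|---|
| 0 | Φ(0.760) = 77.6% | about 77% | about 77% |
| 0.1 | Φ(0.750) = 77.3% | about 77% | about 77% |
| 0.2 | Φ(0.719) = 76.4% | about 76% | about 77% |
| 0.3 | Φ(0.669) = 74.8% | about 75% | about 77% |
| 0.5 | Φ(0.516) = 69.7% | about 70% | about 77% |

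The unadjusted type I error falls to about 4% at 0.3 SD and 3% at 0.5 SD, so the test is conservative.

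**Unequal sequences.** Bias = π·(n1 − n2)/(n1 + n2).
- 20/16 (four losses, all from one sequence): 4/36 = 0.111, so bias is 0.033 SD at π = 0.3 and 0.056 SD at π = 0.5.
- 24/16: 8/40 = 0.2, so bias is 0.06 and 0.10 SD. If allocation to sequence were unblocked (an assumption), a split at least this uneven has a 27% chance. At π = 0.5 the unadjusted type I error is about 6%.

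Averaging the two sequence means removes π exactly, whatever the split.

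**What the sequence check measures.** The natural reading compares within-woman differences between sequences. Its contrast is (τ + π − λA) − (τ − π + λB) = 2π − (λA + λB). With 20 against 20 and no carry-over, its power is 46% at π = 0.3 and 87% at π = 0.5. The bias of the stress estimate from carry-over is (λB − λA)/2, a different quantity, so neither a null nor a positive check settles it. Visit totals by sequence would target λA − λB. That is a between-woman test, with SD of the total = √((1 + r)/(1 − r)). For a carry-over difference of 0.44 SD (a bias of 0.22 SD) its power is 9% to 12% for r from 0.7 to 0.5. The SAP does not mention such a test.

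**The case against.** The strongest reply is that the planned test is valid as it stands. With balanced sequences it is unbiased and conservative, and visit effects of 0.1 to 0.2 SD cost only about 0.2 to 1.2 points of power. A loss of about 8 points needs a visit effect of 0.5 SD, larger than the 0.44 SD target. No document gives a visit effect. All of this stands: for balanced sequences the visit term is a gain in efficiency, not the repair of an invalid test.

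A reader might go further in three ways that the documents do not support.
- *That the sequence check has low power.* Low power belongs to a test on visit totals, which the SAP never proposes. The comparison of within-woman changes is reasonably powered for a visit effect of 0.3 to 0.5 SD.
- *That the stress estimate is biased by a visit effect.* This needs unequal sequences. A split such as 22/14 cannot arise by dropout from 20/20, and the worst split from four losses gives at most about 0.06 SD at the visit effects considered.
- *That carry-over is left unguarded.* The 1-week wash-out in Protocol C.6.3 is the design safeguard, and the task lasts 15 minutes (C.6.4). The documents give no evidence of carry-over.

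The SAP also speaks of estimating the sequence difference, not of a pass-or-fail test, and is silent on what would follow from it. That softens the criticism of the check, but not of the assurance attached to it.

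**Conclusion.** The point holds as a recommended improvement. The primary analysis omits a design factor that was randomised. At 20/20 this costs from nothing to about 8 points of power for visit effects up to 0.5 SD. With 20/16 or 24/16 splits it biases the estimate by 0.03 to 0.10 SD at visit effects of 0.3 to 0.5 SD, which is 8% to 23% of the 0.44 SD target (0.033/0.44 and 0.10/0.44). The claim that the check removes confounding by order is too strong on any reading of the check.

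The sizes rest on assumed visit effects, splits and alpha, and on differences signed as stress minus non-stress. The SAP formula as printed subtracts by visit label (v1 minus v2). Taken literally with balanced sequences, the stress effect would cancel: the mean is (τ + π)/2 + (−τ + π)/2 = π. That is a separate and more basic defect, and correcting the sign alone does not supply the visit term.

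**What to change.** Make the primary Aim 1a analysis, within each meal group, a model of AUC on condition and visit with a random woman effect. With complete pairs this is the same as taking stress-minus-non-stress differences and averaging the two sequence means. Because condition is then coded explicitly, the v1-minus-v2 labelling problem also goes.

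In the sentence on sequence, replace *ensure* with *assess*, name the contrast, and report it with a confidence interval. State whether sequence allocation is blocked.

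A stress contrast from visit 1 only may be added as a descriptive check on carry-over, with its low power stated. The SD of one AUC is 1/√(2(1 − r)), that is 1.00 at r = 0.5 and 1.29 at r = 0.7, so 0.44 becomes 0.44 or 0.34 SD between women. With 20 against 20, power is about 27% or 18%. The visit term itself does not remove carry-over bias, and the wash-out remains the safeguard.

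Cost: SAP wording and one degree of freedom, with no extra measurements. With balanced sequences the loss of power is under 0.1 point. With 24/16 or 22/14 and no visit effect it is about 2 points.
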